
Statistics
	
Three cohorts of patients will be prospectively included in the study:
 
1) Letrozole-stimulated cohort: this includes all newly diagnosed breast cancer who are candidates to receive (neo)adjuvant chemotherapy and undergo oocyte/embryo cryopreservation at the Belgian participating centres.
 
2) Standard-stimulated cohort: this includes all newly diagnosed breast cancer who are candidates to receive (neo)adjuvant chemotherapy and undergo oocyte/embryo cryopreservation at the French participating centres.
 
3) Non-stimulated cohort: this includes all newly diagnosed breast cancer who are candidates to receive (neo)adjuvant chemotherapy who have access

to the Fertility Clinics in all the participating centres but are not willing to undergo oocyte/embryo cryopreservation.

All the efficacy analyses will be performed to compare the letrozole-stimulated cohort and the standard-stimulated cohort. All the safety analyses will be conducted to compare separately the letrozole-stimulated cohort with the non-stimulated cohort and the standard-stimulated cohort with the non-stimulated cohort.

The sample size has been estimated based on the study primary endpoint (i.e. number of mature oocytes collected). With 113 patients in the standard-stimulated cohort and 113 in the letrozole-stimulated cohort, assuming a mean difference of 1.5 in the number of mature oocytes collected between the standard-stimulated cohort and the letrozole-stimulated cohort, the study will have a power of 0.80 to reject the null hypothesis of equal means with a standard deviation of 4.0 and with a significance level (alpha) of 0.05 using a two-sided two-sample equal-variance t-test. Considering that approximately one out of three (1:3) eligible patients counseled to undergo controlled ovarian stimulation for oocyte cryopreservation before starting anticancer treatments will accept the procedure, it is estimated to enroll 339 patients in the non-stimulated cohort.

Patients demographic, clinical and pathologic baseline characteristics will be compared in the three cohorts using chi-square test or Fisher Exact test for categorical variables and Wilcoxon rank-sum test or t-test for continuous variables, as appropriate. Dicothomous outcomes will be compared using

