As suggested by professional guidelines, health care providers have the responsibility to inform patients of the potential development of treatment-related premature ovarian failure and infertility, discuss the available strategies for fertility preservation and refer concerned patients to fertility clinics [2,13–15]. Hence, oncofertility counseling should be considered now as routine clinical practice before the patients start chemotherapy [16].

In young cancer patients, including those with breast cancer, embryo/oocyte cryopreservation are effective and standard options to preserve fertility [2,13–15]. Oocyte cryopreservation requires 3 different phases: induction of multiple follicular growth through controlled ovarian stimulation, oocyte collection performed by ultrasound-guided transvaginal needle aspiration, and evaluation, selection, and vitrification of the oocytes [17,18]. Embryo cryopreservation requires an additional phase consisting in *in vitro* fertilization (IVF) of the collected oocytes [17,18]. Embryo/oocyte cryopreservation must be concluded before starting gonadotoxic anticancer treatments; these strategies are contraindicated in patients already exposed to cytotoxic therapy since a prior exposure to chemotherapy may result in morphologic/genetic abnormalities in the retrieved oocytes and reduced ovarian response to controlled ovarian stimulation [19].

In infertile women without cancer, embryo cryopreservation following controlled ovarian stimulation demonstrated the most reliable results in terms of subsequent pregnancies. The success of the procedure is strongly dependent of patients' age at the time of the procedure: the pregnancy rates according to the 2012 European registers by the European Society of Human Reproduction and Embryology (ESHRE) ranged from approximately 29% in women younger than 35 to 13% in those

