## 5. STATISTICS

Three cohorts of patients will be prospectively included in the study (Figure 1 in the Appendix):

**1) Letrozole-stimulated cohort:** this includes all newly diagnosed breast cancer who are candidates to receive (neo)adjuvant chemotherapy and undergo oocyte/embryo cryopreservation at the Belgian participating centres.

**2) Standard-stimulated cohort:** this includes all newly diagnosed breast cancer who are candidates to receive (neo)adjuvant chemotherapy and undergo oocyte/embryo cryopreservation at the French participating centres.

**3) Non-stimulated cohort:** this includes all newly diagnosed breast cancer who are candidates to receive (neo)adjuvant chemotherapy who have access to the Fertility Clinics in all the participating centres but are not willing to undergo oocyte/embryo cryopreservation. Patient who underwent another fertility preservation procedure (ovarian tissue cryopreservation, GnRH analogues,...) are eligible in this cohort.

All the efficacy analyses will be performed to compare the letrozole-stimulated cohort and the standard-stimulated cohort. All the safety analyses will be conducted to compare separately the letrozole-stimulated cohort with the non-stimulated cohort and the standard-stimulated cohort with the non-stimulated cohort.

To evaluate the efficacy of performing a controlled ovarian stimulation with or without letrozole in young women with newly diagnosed breast cancer who are candidates to receive (neo)adjuvant chemotherapy, the following endpoints will be assessed:

- Number of mature oocytes collected (primary endpoint).
- Number of oocytes collected;
- Maturation rate: defined as ratio between the number of mature oocyte collected and total number of oocyte collected;
- Number of oocyte/embryo cryopreserved;
- Number of patients with poor response: defined as retrieval of  $\leq 4$  oocytes;
- Number of patients with stimulation failure: defined as no follicular growth after 1 week of adequate controlled ovarian stimulation administration.

The efficacy of performing controlled ovarian stimulation with or without letrozole will be evaluated also in various subgroups of young women with newly diagnosed breast cancer who are candidates to receive (neo)adjuvant chemotherapy according to the following characteristics:

- Type of stimulation: follicular vs. random;
- Hormone receptor status: positive vs. negative;
- Presence of *BRCA* mutation: *BRCA*-mutated vs. *BRCA*-not mutated.

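### Do the cohort definitions leave women who start stimulation but have no retrieval, or nothing frozen, out of the primary comparison?

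*Combined protocol and SAP*

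**What the plan says.** The Synopsis and Section 5 sort the stimulated women by country. The letrozole-stimulated cohort consists of candidates for chemotherapy who "undergo oocyte/embryo cryopreservation at the Belgian participating centres"; the standard-stimulated cohort consists of those who "undergo oocyte/embryo cryopreservation at the French participating centres". The third cohort attends the same fertility clinics "but are not willing to undergo oocyte/embryo cryopreservation". Section 5 refers to a figure for the cohort structure: "Three cohorts of patients will be prospectively included in the study (Figure 1 in the Appendix").

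All efficacy analyses compare the two stimulated cohorts. The primary endpoint is the number of mature oocytes collected. Among the secondary efficacy endpoints are:

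- "Number of patients with stimulation failure: defined as no follicular growth after 1 week of adequate controlled ovarian stimulation administration";
- "Number of patients with poor response: defined as retrieval of" four oocytes or fewer;
- "Maturation rate: defined as ratio between the number of mature oocyte collected and total number of oocyte collected".

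Section 3.2 lists poor response and stimulation failure for collection, together with type of start, total FSH dose, stimulation days and antagonist days. Neither that list nor the protocol characteristics in Section 5 names letrozole.

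**The concern.** Three gaps appear on first reading.

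1. **Cohort membership.** If undergoing cryopreservation means that something was frozen, a woman whose stimulation fails is in neither stimulated cohort. She is not in the third cohort either, since she was willing. The primary comparison would then be conditioned on something that happens after stimulation starts, and unequal failure rates would distort the difference in mature oocytes. The safety comparisons would be restricted in the same way.
2. **Scoring.** No sentence says whether a cycle without retrieval counts as 0 mature oocytes, as missing or as excluded, or whether it is a poor response. Its maturation rate is 0/0.
3. **Exposure.** Letrozole gives one cohort its name but is not a listed data item, so exposure in Belgium is inferred from country.

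At stake would be a biased primary estimate, and room to choose between exclusion and a score of 0 after seeing the data.

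**Working it through.** **Which reading does the plan support?**

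| Place | What it implies |
|---|---|
| Section 5, efficacy endpoints | Stimulation failure is compared between the two stimulated cohorts. Under the literal reading a woman with no follicular growth could never be in either, so the endpoint would always be 0. |
| Section 1 | "Oocyte cryopreservation requires 3 different phases: induction of multiple follicular growth through controlled ovarian stimulation". Undergoing the procedure can therefore mean entering it. |
| Section 3.1 | The ovarian-reserve criterion applies to women who have stimulation with cryopreservation as its purpose. |
| Section 3.2 | Data are entered for all consecutive eligible patients included, and stimulation failure is an item. |
| Sections 4.3 and 4.4 | Enrolment samples are taken before stimulation starts. |
| Section 5, safety endpoints | Survival times run from study inclusion. |
| Section 5, sample size | The split between stimulated and non-stimulated women rests on who accepts the procedure, which matches the unwillingness that defines the third cohort. |
| Section 8.2 | Records are also completed for women who do not finish the study. |

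Nothing in the plan states an exclusion. The inclusive reading is the only one under which the failure endpoint means anything.

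**The plan's own figure.** Inputs from Section 5: 113 per cohort, means 6.1 and 7.6, SD 4.0, two-sided alpha 0.05, equal-variance t-test.

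- SE = 4.0 × √(2/113) = 0.532, and 1.5/0.532 = 2.82.
- Noncentral-t power is 0.801 (0.798 at 112). The stated 0.80 is reproduced.

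**How much would the literal reading cost?** The documents give no failure rate, so the rates p below are assumptions. At 113 starters, 2%, 5% and 10% are 2.3, 5.7 and 11.3 women. Suppose the all-starter means are truly equal at 6.1, with SD 4.0 among completers. The completer mean is then 6.1/(1 − p).

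| Assumed p in the two cohorts | Completers | Spurious difference | SE | Ratio | Rejection probability |
|---|---|---|---|---|---|
| equal | equal | 0 | – | 0 | 0.050 |
| 5% vs 2% | 107, 111 | 6.42 − 6.22 = 0.20 | 0.542 | 0.36 | 0.065 |
| 10% vs 5% | 102, 107 | 6.78 − 6.42 = 0.36 | 0.554 | 0.64 | 0.098 |

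Swapping the rates reverses the sign.

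**What does the inclusive reading do to power?** If 6.1, 7.6 and SD 4.0 already include failed cycles, power stays at 0.80. If they describe completers, each failure adds a 0: mean = (1 − p)m and variance = (1 − p) × 4.0² + p(1 − p)m², with 113 per cohort.

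| Assumed p, standard / letrozole | Difference | Power |
|---|---|---|
| 2% / 2% | 0.98 × 1.5 = 1.47 | 0.77 |
| 5% / 5% | 0.95 × 1.5 = 1.43 | 0.72 |
| 10% / 10% | 0.90 × 1.5 = 1.35 | 0.65 |
| 5% / 10% | 6.84 − 5.80 = 1.05 | 0.45 |
| 10% / 5% | 7.22 − 5.49 = 1.73 | 0.87 |

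With unequal rates the all-starter difference itself changes, because failures are part of the efficacy being compared. That is not a bias.

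**Letrozole.** Section 4.1 makes letrozole part of the Belgian schema, and Section 1 says that it cannot be used for stimulation in France. No passage suggests Belgian cycles without it. Section 8.1 names pharmacy dispensing records among the source documents. The eCRF and the appendix figure are not available to this review, so absence from the protocol's list does not show absence from the data.

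**The case for a change.** The strongest case for a change is that inferred intent is not an analysis set. Even on the inclusive reading, the plan does not say that a cycle without retrieval scores 0 or counts as a poor response. Cycles cancelled for reasons other than absent growth, and retrievals of more than four oocytes with nothing frozen, have no category of their own. A sentence written in advance would cost little and would remove a choice that moves both estimate and power, as the second table shows.

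Much of this is accurate: the sentence is missing and would be cheap. It does not show an error in the plan, because the choice it would settle is hardly open:

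- The primary endpoint counts oocytes collected, and a cycle without retrieval collects none.
- The failure endpoint already needs all starters in its denominator.
- A retrieval that yields no oocytes meets the poor-response definition arithmetically.
- A retrieval with nothing frozen still has an observed mature-oocyte count.
- The 0/0 case touches one secondary ratio, which can be calculated only where at least one oocyte was collected.

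The bias scenario is also artificial. To hold the all-starter means equal, the cohort with more failures must have an exactly offsetting higher yield among its completers (6.78 against 6.42 at 10% against 5%), and nothing in the documents points that way.

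**Conclusion.** The concern does not call for a change. The cohort wording is loose, but the failure endpoint, the description of the procedure, the timing of enrolment and the acceptance-based sizing all put women who start stimulation in the stimulated cohorts. What remains is unstated detail that an analyst would supply in the obvious way: all starters analysed, 0 mature oocytes when none is collected, and maturation rate among women with at least one oocyte.

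Harm to the primary comparison needs both the literal reading and unequal failure rates. At the assumed rates it is 0.20 to 0.36 oocytes against a planned difference of 1.5, with a false-positive rate of 0.065 to 0.098, which is modest. The documents give nothing to size an effect on the safety comparisons. The power range of 0.45 to 0.87 under the inclusive reading depends on assumed failure rates and on the planning means describing completers, which Section 5 does not say; otherwise power is 0.80. The letrozole point is a gap in a protocol-level list. It is confined to Belgium, and there is no sign that Belgian cycles go without the drug.

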### 3.2. Data collection

For all consecutive eligible patients included in the study, anonymized data will be entered into ad hoc electronic Case Report Forms (eCRF). The following information will be collected:

1) Baseline characteristics (at study inclusion): BMI; smoking habit; age at menarche; use of birth control pills; prior children before breast cancer diagnosis; history of spontaneous or induced abortion; prior treatment for infertility; prior gynecological surgery and/or medical history with possible impact on fertility; baseline AMH value.

- 2) Breast cancer history: date of diagnosis; age at diagnosis; disease stage; type of breast and axillary surgery; histology; tumor size and nodal status (for patients who underwent primary systemic therapy, both clinical tumor size and nodal status before treatment initiation and pathological tumor size and nodal status at the time of surgery will be collected); grade; hormone receptor status (estrogen and progesterone receptors); HER2 status.
- 3) Treatment of the primary tumor: timing of systemic therapy administration (adjuvant or neoadjuvant); use of chemotherapy (type and number of cycles); use of endocrine therapy (type and duration); use of anti-HER2 targeted therapy (type and duration); use of radiotherapy; use of breast reconstruction surgery.
- 4) Survival status: any recurrence of invasive breast cancer including date of the event; type of recurrence of invasive breast cancer (locoregional or distant event); any second primary contralateral breast cancer including date of the event; any second primary malignancy including date of the event; date of last follow-up and/or death.
- 5) Controlled ovarian stimulation protocol: type of stimulation (follicular or random); total FSH dose; number of stimulation days; number of days with antagonist; estradiol and progesterone levels at triggering and during luteal phase (L3-L8); number of oocyte/embryo collected; number of mature oocytes collected; maturation rate; number of oocyte/embryo cryopreserved; number of patients with poor response; number of patients with stimulation failure.
- 6) Ovarian function before and after chemotherapy: treatment-induced amenorrhea; age at menopause; AMH values.
- 7) Pregnancy after breast cancer: any pregnancy including date of the event; pregnancy outcome; gestational age at delivery; pregnancy/fetal/obstetrical outcomes; breastfeeding and its duration; use and type of assisted reproductive technology.

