8) Presence of germline *BRCA* mutation or other type of germline mutations (if available): date of genetic testing; type of mutation; use and date of breast prophylactic surgery; use and date of gynecological prophylactic surgery.

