- Type of stimulation: follicular or random;
- Total follicle-stimulating hormone (FSH) dose;
- Number of stimulation days;
- Number of days with antagonist;
- Progesterone and Estradiol levels at trigger;
- Progesterone level at triggering and during luteal phase (if available).

In patients who return to the fertility clinic after the end of treatment, to evaluate the type and outcomes of assisted reproductive technology procedures used, the following endpoints will be evaluated:

- Number of patients who returned to fertility clinic;
- Type of assisted reproductive technology procedures used;
- Number of embryos transferred;
- Pregnancy rate: defined by  $\beta$ -hCG determination 14 days after embryo transfer;
- Clinical pregnancy rate: defined as the presence of at least one gestational sac at the time of the first ultrasound examination by the eight week of gestation;
- Implantation rate per embryo transfer: defined as the ratio between the number of visible sacs 4 weeks after embryo transfer and the number of embryos transferred.

In patients with a clinically confirmed pregnancy obtained with assisted reproductive technology procedures after the end of treatment, pregnancy, fetal and obstetrical outcomes of the pregnancies will be evaluated. The following endpoints will be evaluated:

- Miscarriage rate;
- Live birth rate per embryo transfer: defined as the number of births of live infants beyond viability (> 24 weeks);
- Twinning rate;
- Premature delivery: <37 weeks of gestation;
- Malformation rate with number and types of malformations;
- Obstetrical complication rate with number and types of complications.

Finally, to evaluate the impact of anticancer therapies (chemotherapy with or without endocrine therapy with or without anti-HER2 agents) on patients' ovarian function, the following endpoints will be evaluated:

- Incidence of treatment-induced amenorrhea one year after the end of chemotherapy;
- Incidence of treatment-induced amenorrhea two years after the end of chemotherapy;

- Incidence of treatment-induced amenorrhea five years after the end of chemotherapy;
- Age at menopause defined as no menstrual period for more than 12 months irrespectively of menstrual resumption after chemotherapy;
- AMH values one year after the end of chemotherapy;
- AMH values two years after the end of chemotherapy;
- AMH values five years after the end of chemotherapy.

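### Section 3.2 lists no field for other fertility-preservation procedures allowed in the non-stimulated cohort, so the secondary ovarian-function results may be confounded to an unknown extent and direction

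*Combined protocol and SAP*

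**What the plan says.** Section 5 defines the non-stimulated cohort as women who attend a participating fertility clinic but decline oocyte or embryo cryopreservation. It then adds: "Patient who underwent another fertility preservation procedure (ovarian tissue cryopreservation, GnRH analogues,...) are eligible in this cohort". The list is open-ended. This is the largest cohort, with 339 of 565 planned women.

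Section 5 also sets the secondary aim "to evaluate the impact of anticancer therapies (chemotherapy with or without endocrine therapy with or without anti-HER2 agents) on patients' ovarian function". Its endpoints include "Incidence of treatment-induced amenorrhea one year after the end of chemotherapy", the same measure at two and five years, AMH at one, two and five years, and age at menopause. The aim is not confined to one cohort.

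Section 3.2 sets out eight groups of data. The items closest to the permitted procedures are:
- group 1, headed "Baseline characteristics (at study inclusion" (time point in parentheses), which includes "prior gynecological surgery and/or medical history with possible impact on fertility";
- group 3, on treatment of the primary tumour, which includes "use of endocrine therapy (type and duration" (closing parenthesis omitted);
- group 6, which reads "Ovarian function before and after chemotherapy: treatment-induced amenorrhea; age at menopause; AMH values";
- group 8, on germline mutations, which includes "use and date of gynecological prophylactic surgery".

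**The concern.** The plan names two procedures in advance, allows both in its largest cohort, and does not list either among the data to be collected. Both bear on the ovarian-function endpoints. Section 4.3 uses AMH as the measure of ovarian reserve, and taking ovarian tissue may change AMH directly. GnRH analogues are listed in Section 5 as a fertility-preservation procedure, so the plan itself treats them as something meant to affect later ovarian function.

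If the exposure is not recorded, an analyst following the plan cannot tell how much of a change in AMH or menses belongs to chemotherapy, endocrine therapy or anti-HER2 therapy and how much to the procedure. The results at stake are those a clinician would use to counsel a young woman about what treatment does to her ovaries.

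**Working it through.** **1. Does any listed item capture the exposure?** Taking Section 3.2 group by group:
- Group 1 asks about earlier gynaecological surgery and is completed at inclusion. Section 4.3 equates enrolment with the time of oncofertility counselling or diagnosis. A harvest before inclusion would be caught. One that follows the counselling would not.
- Group 3 records the type and duration of endocrine therapy, under the heading of treating the primary tumour. A GnRH analogue given as cancer treatment should appear. One given for ovarian protection may or may not be entered, and purpose is not asked.
- Group 5 describes the stimulation cycle, which this cohort does not have.
- Group 6 lists outcomes, not exposures.
- Group 7 covers assisted reproduction in connection with pregnancy after cancer.
- Group 8 covers prophylactic surgery only.
- Groups 2 and 4 concern the tumour and survival.

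Table 1 adds blood and tissue samples only. No item is dedicated to the exposure, and two overlap with it in part.

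**2. Would the timing let baseline AMH absorb the effect?** Section 4.3 places the first AMH sample at enrolment and the next at the end of chemotherapy. A harvest between counselling and chemotherapy falls between the two. Any change it causes is part of the change from baseline, and adjusting for baseline AMH does not remove it.

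**3. Does the analysis separate these women?** The ovarian-function subgroups in Section 5 are age, type and length of chemotherapy, platinum, endocrine therapy, anti-HER2 therapy and BRCA status. None is by fertility-preservation procedure. Endocrine therapy enters only as use or no use. Binary outcomes go to logistic regression with no covariates named, and no model is named for AMH as an outcome. No exclusion or sensitivity analysis is given.

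**4. Is the sample size affected?** No. From Section 5: difference 1.5, SD 4.0, two-sided alpha 0.05, power 0.80. The normal approximation gives n = 2 × (1.960 + 0.842)² × 4.0² / 1.5² = 111.6, so 112 per cohort. The exact t-test gives 112.6, so 113, with power 0.801 at 113. The plan's figure is reproduced, and it concerns only the two stimulated cohorts.

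**5. How large could the effect be?** The documents give no uptake and no effect size, so every value below except 339 and 565 is an assumption. Users are taken to lie only in the non-stimulated cohort, and users and non-users are taken to be otherwise alike.

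Amenorrhoea: shift in the cohort rate = f × d, where f is the share of users and d the change in their risk. Over all women, multiply by 339/565 = 0.60.

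| f (women) | d (either direction) | Shift, 339 women | Shift, 565 women |
|---|---|---|---|
| 5% (17) | 10 points | 0.5 points | 0.3 points |
| 10% (34) | 20 points | 2 points | 1.2 points |
| 30% (102) | 20 points | 6 points | 3.6 points |
| 50% (170) | 20 points | 10 points | 6 points |

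Mean AMH: relative fall = f × r, where r is the proportional loss after tissue removal. With f = 10% and r = 30% it is 0.10 × 0.30 = 3%. With f = 30% and r = 50% it is 0.30 × 0.50 = 15%. Over all 565 women these become 3% × 0.60 = 1.8% and 15% × 0.60 = 9%.

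**The case against.** The strongest reply is that the gap is in a protocol list, not shown to be in the data. The eCRF is not among the documents, and Section 8.1 requires source records to be kept, so the information may be recoverable. A reader might infer that the variable does not exist and that adjustment is impossible. The documents show only that Section 3.2 does not list it. The two partly overlapping items also count for something, and it is an inference that sites would leave out a protective GnRH analogue. This part of the reply stands and limits the wording to what the list may miss. It does not close the gap, because a harvest after inclusion falls outside both items and consistent recording cannot be expected without a dedicated field.

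A second reply is that bias has not been demonstrated. A reader might infer that procedure effects will be reported as treatment effects, in a known direction. That would need uptake and effect sizes that the plan does not give. The two exposures could also pull in opposite directions: lost tissue might make ovarian damage look worse, while a protective analogue might make it look milder. This stands in full.

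Third, a reader might extend the point to iDFS, BCFI and OS, since the same cohort is the comparator there. The documents offer no mechanism or size for such an effect. Dropping GnRH-analogue users from iDFS would also create a problem of its own. Section 5 times iDFS from inclusion, and the analogue may start later, so the exclusion would condition on something that happens after time zero.

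Finally, admitting these women is an explicit choice and only secondary aims are touched. That is true, but the objection here is to not recording the procedures, not to admitting the women.

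**Conclusion.** The point holds in a limited form. The plan permits named fertility-preservation procedures in a cohort of 339, lists no field for them, and has no analysis that separates the women who had them. AMH, amenorrhoea and age at menopause, which the plan attributes to anticancer therapy, may therefore be confounded.

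Extent and direction are unknown. The illustrative ranges (0.5 to 10 points of amenorrhoea, 3% to 15% of mean AMH, both within the non-stimulated cohort) rest wholly on assumed uptake and effects. They show that the shift could be negligible or material, not that it is either. The conclusion assumes that the eCRF follows Section 3.2. If it already holds the field, what remains is to say so in Section 3.2 and to specify the analysis.

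The documents do not support a claim of certain bias or a claim about survival outcomes. The primary comparison of mature oocytes and its sample size are untouched. The change should be made, because the exposure is foreseen and is more reliably recorded as it happens than reconstructed at the five-year analysis.

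**What to change.** In Section 3.2, add for all three cohorts:
- other fertility-preservation procedure (none, ovarian tissue cryopreservation, GnRH analogue, other), with date;
- for GnRH analogues, start, stop and purpose.

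All three cohorts need the item because nothing in the documents rules out a GnRH analogue during chemotherapy in a stimulated woman. Purpose matters because Section 4.1 already uses GnRH agonists to trigger ovulation, and because group 3 may record the same class of drug as endocrine therapy.

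In Section 5, pre-specify that:
- women with ovarian tissue removed are analysed separately for AMH, or excluded in a sensitivity analysis;
- GnRH-analogue use is a covariate or stratum in the amenorrhoea and AMH analyses.

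No exclusion of GnRH-analogue users from iDFS should be added.

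The cost is one extra eCRF item, a few lines in Section 5, and slightly fewer women in the separated AMH analysis. No visit, sample or patient is added, and eligibility and care do not change. Adjustment will separate the recorded exposure but will not remove differences between women who choose a procedure and those who do not, and the report should say so.
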